A RANDOMIZED CONTROLLED PILOT TRIAL OF A STRUCTURED MOBILE TECHNOLOGY BASED LIFESTYLE PROGRAM VS USUAL CARE FOR PATIENTS WITH NON-ALCOHOLIC FATTY LIVER DISEASE

Protocol Number: HUM 00153750

National Clinical Trial (NCT) Identified Number: TBA

Principal Investigator: [name] MD MSc

Sponsor: University of Michigan

Grant Title: American Association for the Study of Liver Diseases (AASLD) Clinical Translational and Outcomes Research Award (CTORA)

NCT Number: NCT03839082

Grant Number: AWD007197

Funded by: AASLD

Version Number: 3.0

Version Approval Date: 12 November 2019

Summary of Changes from Previous Version:

Affected Section(s)	Summary of Revisions Made	Rationale
Section 1.2	Goal total number of participant was increased from 100 to 120 subjects. Hence, the number of patient in each arm of the study will be 60.	This change is necessary in order to ensure that we have more accurate mean values and provide smaller margin of error.
Section 5.5	Additional recruitment strategies were added. Potential patients will be identified through data direct, EMERSE as well as our general hepatology clinics. Potential participants identified via data direct and our general hepatology clinics will be recruited via phone and text.	Changes will help increase efficiency and speed of recruitment.

Table of Contents

INVES	STIGATOR'S SIGNATURE	
1	PROTOCOL SUMMARY	
1.1	Synopsis	
1.2	Schema	
1.3	Schedule of Activities	3
2	INTRODUCTION	
2.1	Study Rationale	
2.2	Background	
2.3	Risk/Benefit Assessment	
2.	.3.1 Known Potential Risks	
2.	.3.2 Known Potential Benefits	
2.	.3.3 Assessment of Potential Risks and Benefits	6
3	OBJECTIVES AND ENDPOINTS	6
4	STUDY DESIGN	
4.1	Overall Design	
4.2	Scientific Rationale for Study Design	
4.3	Justification for Intervention	
4.4	End-of-Study Definition	
5	STUDY POPULATION	
5.1	Inclusion Criteria	
5.2	Exclusion Criteria	
5.3	Lifestyle Considerations	
5.4	Screen Failures	
5.5	Strategies for Recruitment and Retention	
6	STUDY INTERVENTION(S) OR EXPERIMENTAL MANIPULATION(S)	
6.1	Study Intervention(s)	
	.1.1 Study Intervention or Experimental Manipulation Description	
6.2	Fidelity	
6.	.2.1 Interventionist Training and Tracking	
6.3	Measures to Minimize Bias: Randomization and Blinding	
6.4	Study Intervention/Experimental Manipulation Adherence	
6.5	Concomitant Therapy	
7 PART	STUDY INTERVENTION/EXPERIMENTAL MANIPULATION DISCONTINUATION AND ICIPANT DISCONTINUATION/WITHDRAWAL	

1 PROTOCOL SUMMARY

1.1 SYNOPSIS

Title:	A Randomized Controlled Pilot trial of a Structured Mobile Technology Based Lifestyle Program Vs Usual Care for Patients with Non-Alcoholic
	Fatty Liver Disease
Grant Number:	AWD007197
Study Description:	Lifestyle interventions remain first line therapy for the treatment of
Study Description.	non-alcoholic fatty liver disease (NAFLD). In clinical practice, it is challenging for patients to initiate and maintain these changes. In this randomized clinical pilot trial, we will evaluate impact of a structured mobile technology-based lifestyle intervention program compared to usual care to among patients with NAFLD. We hypothesize individuals randomized to the intervention arm will have significantly improved
	outcomes compared to usual care, and that the intervention will be
	feasible, low cost and amenable to large scale implementation.
Objectives:	Primary objective: compare the effectiveness of usual care to a mobile technology based lifestyle intervention on change in liver and metabolic related parameters.
	Secondary objectives: identify predictors associated with reduction in hepatic steatosis and weight loss.
Endpoints:	Primary Endpoint: change in amount of hepatic steatosis
	Secondary Endpoints: change in weight, change in physical activity
Study Population:	120 adult patients with NAFLD including steatosis only, non-alcoholic steatohepatitis (NASH) and NAFLD-related compensated cirrhosis seen in the Michigan Medicine Hepatology clinic.
Phase or Stage:	N/A
Description of Sites/Facilities Enrolling	
Participants:	Michigan Medicine Hepatology Clinics, and patient identified through
i il cicipantor	Data Direct and EMERSE in various local clinics
Description of Study	
Intervention/Experimental	Personalized adaptive lifestyle intervention program that includes
Manipulation:	physical activity and nutritional feedback compared to usual care
Study Duration:	18 months
Participant Duration:	13 months

1.2 SCHEMA

[figure not shown]

Figure 1. All participants will be enrolled in the study for ~12 months and will complete 3 study visits. Individuals randomized to the Intervention arm will have 6 months of intervention followed by 6 months of follow-up to assess for behavior change maintenance. Individuals randomized to the Usual Care Waitlist will be followed for 6 months, after which they will start a 6-month intervention period.

1.3 SCHEDULE OF ACTIVITIES

Table 1 - Arm 1 - active intervention w/follow up

OnCore Calendar Segment	Pre-study	Consented OnStudy OnArm/OnTreatm	On treatment	On FollowUp	OffStudy
Study Timeline	Pre-screening (Pre-consent)	Visit 1 Day 1	Phone Call- Intervention Arm Day 84 ±7	Visit 2 Day 168 ±14	Visit 3 Day 336 ±21
EMR Review Eligibility	х				
Informed Consent		Х			
Demographics		Х			
Clinical history		Х			
Randomization		Х			
Provide FitBit and Instruction to Intervention Arm		х		х	
Outcome Evaluation					
Vitals + Anthropometrics: blood pressure, height, weight, waist and hip circumference		х		х	х
Blood Work: ¹ hepatic panel, platelets, A1c, fasting insulin, glucose, lipid panel		х		х	х
6MWT		х		х	х
Hand Grip Strength		х		х	х
Quality of Life Questionnaire		Х		х	х
Physical Activity Survey (IPAQ)		х		х	х
Motivation to Change Questionnaire		Х		х	х
Dietary Survey		Х	Х	х	х
Dietician Assessment ²		Х			
VCTE ¹		Х		х	х
MRE1 ^{1,3}		Х		Х	
Exit Interviews				Х	х
Adverse Events Reporting		x	Х	х	х

Version <3.0>
12 NOVEMBER 2019

		p		nent	
OnCore Calendar Segment	Pre-Study	Consented OnStudy		OnTreatment	Off Study
Study Timeline	Pre-screening (Pre-consent)	Visit 1 Day 1	Visit 2 Day 168 ±7	Phone Call- Intervention Arm Day 252 ±14	Visit 3 Day 336 ±21
EMR Review Eligibility	х				
Informed Consent		х			
Demographics		х			
Clinical history		х			
Randomization		х			
Provide FitBit and Instruction to Intervention Arm		х	х		
Outcome Evaluation					
Vitals + Anthropometrics: blood pressure, height, weight, waist and hip circumference		х	х		х
Blood Work: ¹ hepatic panel, platelets, A1c, fasting insulin, glucose, lipid panel		х	х		х
6MWT		Х	х		х
Hand Grip Strength		х	х		х
Quality of Life Questionnaire ⁴		х	х		х
Physical Activity Survey (IPAQ) ⁴		х	х		х
Motivation to Change Questionnaire ⁴		х	Х		х
Dietary Survey ⁴		х	Х	х	х
Dietician Assessment ²		х			
VCTE ¹		х	Х		х
MRE1 ^{1,3}		х	Х		
Exit Interviews			Х		х
Adverse Events Reporting		х	Х	Х	х

Table 2. Arm II - wait list control; receives intervention after visit 2

¹Baseline results can be abstracted from medical record if performed within prior 6 months and <5% weight change since that time. Otherwise, VCTE will be performed +/- 14 days from enrollment. Hepatic panel and platelet count are standard of care measures. Remainder of imaging and laboratory data will be research costs. ²Can be done +/- 14 days from enrollment in person or via telephone

³ Only done in half of patients due to cost, determined by computer randomization with stratification according to liver disease stage (cirrhosis)

⁴ If not enough time during enrollment, participants will be sent a link via email to complete the surveys within 14 days from enrollment date.

EMR, electronic medical record; 6MWT, 6 minute walk test; IPAQ, International Physical activity Questionnaire; VCTE, vibration controlled transient elastography; MRE, magnetic resonance elastography

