4 STUDY DESIGN

4.1 OVERALL DESIGN

This randomized clinical pilot trial will compare a mobile technology-based lifestyle intervention to a waitlist control group receiving usual care for adult patients with NAFLD. The intervention will use FitBit to track and promote physical activity through tailored longitudinal feedback. Patient will also receive nutritional counseling with serial nutritional assessments. The primary endpoint will be change in amount of hepatic steatosis. Secondary outcomes include changes in weight and physical activity (assessed by trend in step counts). A wait-list control design will be applied. 60 Patients will be randomized to the intervention arm for 6 months and 60 to usual care (the wait-list control). Those initially randomized to the intervention arm will then transition to a 6-month post intervention monitoring period to assess maintenance of behavior change and sustainability of impact on outcomes of interest. Individuals initially randomized to usual care, will transition to the intervention at month 6 for a total of 6 months.

The intervention arm will receive tailored physical activity and nutritional counseling, and the waitlist control arm which will follow usual and customary care for NAFLD patients attending our Heptology clinic for 6 months and then receive the 6-month intervention.

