4.2 SCIENTIFIC RATIONALE FOR STUDY DESIGN

This trial will incorporate a wait-list control that will allow us to maximize our ability to assess the primary outcome (by using a pre-post intervention analysis). The 6-month post-intervention follow-up among those initially randomized to the intervention will allow us to assess maintenance of behavior change.

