6 STUDY INTERVENTION(S) OR EXPERIMENTAL MANIPULATION(S)

6.1 STUDY INTERVENTION(S)

6.1.1 STUDY INTERVENTION OR EXPERIMENTAL MANIPULATION DESCRIPTION

This is a randomized trial comparing a structured mobile technology-based lifestyle intervention compared to usual care.

Intervention

-Education: Patients in the intervention arm will receive our NAFLD educational folder with an overview of contents by study staff. The folder includes: 1) NAFLD disease information including diagnosis, clinical manifestations, natural history and treatments; 2) NAFLD nutritional recommendations including sample menus; 3) NAFLD physical activity recommendations including walking programs and physical activity logs; 4) weight tracking logs; and 5) resources for diet and exercise programs.

-**Physical Activity**: All participants in the intervention arm (N=60) will receive a FitBit Zip for monitoring of step counts. The Fitbit wirelessly syncs data from the tracker to the Fitbit software or app. Study staff will assist with downloading the software and will instruct participants to wear their FitBit during waking hours every day. At any time if the participant has questions or problems regarding the use of the FitBit, a study staff member can be contacted. Study staff will retrieve users' step count data for analysis weekly and will provide subject with personalized feedback on physical activity with tailored step count goals (10% increase per week with max increase 800 steps per week to a maximum of 10,000 steps/week) and motivational messaging via e-mail. Patients with consecutive days without data recorded or with other signs of low FitBit usage (days with minimal step counts) will be contacted by study staff via e-mail or phone if necessary to encourage use. Feedback will occur weekly for the first 3 months of the intervention and then transition to biweekly for the last 3 months. Participants will also complete the short-version IPAQ for physical activity at enrollment, 6 month and 12 month follow-up visits.

-Nutrition: Patients in the intervention arm will have a nutritional assessment by a GI nutritionist specializing in NAFLD either at the enrollment visit if time allows, or in a separate in person or phone assessment within the first 2 weeks of enrollment. All patients will also complete the "Starting the Conversation" nutritional questionnaire for patients with metabolic disease at enrollment, 6 month and 12 month follow-up visits.(15)

Usual Care

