At our center, patients with NAFLD /NASH without decompensated cirrhosis are seen every 6-12 months. Visits are approximately 15-20 minutes and consist of review of BMI/weight, recent hepatic panel and Fibroscan if ordered. Management typically consists of a breif overview of lifestyle changes including improvements in nutrition and physical actiity. Vitamin E is prescribed In a small proportion of patients. A similarly small proportion of patients are formally referred to and subsequently evaluated by a nutritionist.

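### The waitlist schedule places the dietitian assessment, an intervention component, at enrollment and never at crossover

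*Combined protocol and SAP*

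**What the plan says.** Section 1.3 has one schedule per arm. The second is labelled "Table 2. Arm II - wait list control; receives intervention after visit 2". Its Dietician Assessment row is marked at Visit 1 (Day 1), the same column as randomization, and is blank at Visit 2, at the phone call and at Visit 3. Footnote 2 lets the assessment be done within 14 days of enrollment, with no separate timing for this arm.

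Section 6.1.1 places the assessment under the intervention: "Patients in the intervention arm will have a nutritional assessment by a GI nutritionist specializing in NAFLD". Of usual care the same section says: "A similarly small proportion of patients are formally referred to and subsequently evaluated by a nutritionist".

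On timing for controls, section 1.2 says: "Individuals randomized to the Usual Care Waitlist will be followed for 6 months, after which they will start a 6-month intervention period". Section 4.1 agrees: "Individuals initially randomized to usual care, will transition to the intervention at month 6 for a total of 6 months". Section 6.3 says the same. Section 4.2 justifies the waitlist design because it will "maximize our ability to assess the primary outcome (by using a pre-post intervention analysis").

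**The concern.** The trial compares tailored activity feedback plus nutritional counseling with usual care over six months. The dietitian assessment is the only dietitian contact scheduled in either arm. If controls also receive it at enrollment, that scheduled difference between the arms disappears before the primary endpoint is measured.

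Three things are at stake:

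- The 6-month comparison of CAP would tend to be narrowed.
- Controls would have no dietitian contact scheduled when their own intervention begins, so the two arms would not receive the same program.
- For controls, the Visit 2 value that serves as the starting point of the pre-post analysis would already follow a dietitian contact.

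**Working it through.** The plan states no figure to reproduce on this point. The check compares the schedules with the text, plus some day arithmetic.

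**1. Is the row read correctly?** Table 2's columns are pre-screening, Visit 1, Visit 2, phone call and Visit 3. Neighboring rows fall where they should: the dietary survey at all four contacts from Visit 1 on, and MRE at Visits 1 and 2. The dietitian row has one mark, at Visit 1, which agrees with footnote 2's reference to enrollment.

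**2. Was Table 2 adapted for the delayed start?** In part. Section 8.1 sets the phone call after 3 months of intervention.

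- Arm 1 call: Day 84.
- Arm II call, from the header "Phone Call- Intervention Arm Day 252 ±14": 252 − 168 = 84 days after Visit 2.

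The call was moved by 252 − 84 = 168 days. The dietitian row was moved by 0 days and is identical to Table 1.

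**3. Contacts scheduled, by arm**

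| | Arm 1 | Arm II as written | Arm II per design text |
|---|---|---|---|
| Dietitian contact at enrollment | 1 | 1 (60 of 60 controls) | 0 beyond usual care |
| Dietitian contact at start of own intervention | 1 (the same contact) | 0 | 1 |

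**4. Gap between the contact and the controls' intervention.** Taking the contact at Day 1 to Day 15, and Visit 2 at Day 168 ± 7, that is Day 161 to Day 175:

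- shortest: 161 − 15 = 146 days
- longest: 175 − 1 = 174 days

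**5. Two companion points**

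- *FitBit row.* The row "Provide FitBit and Instruction to Intervention Arm" carries the same Visit 1 and Visit 2 marks in both tables. In Table 2 the Visit 1 mark may be a shared row carried over, or a device given to measure step counts. The table does not say which.
- *Step ceiling.* Section 6.1.1 caps the goal at 10,000 steps per week: 10,000 / 7 = 1,429 steps per day. The 800-step limit on increases overtakes the 10% rule at 800 / 0.10 = 8,000 steps, just below 10,000, so the rule hangs together if both figures are in one unit. Read as weekly, the 800-step limit would be 800 / 7 = 114 steps per day. Section 6.4 counts valid FitBit days in steps per day, so a daily unit is almost certainly meant.

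**The case against.** The strongest counter-reading is that the mark is a baseline measurement. In both tables the row sits below the Outcome Evaluation heading, and section 4.1 words counseling and assessment separately. On that reading, moving the mark would delete baseline data for controls. This does not hold. Section 6.1.1 restricts the nutritionist assessment to the intervention arm, and in the same paragraph gives every patient a separate dietary questionnaire, which has its own row. The assessment is never repeated in either table, so it cannot measure change. The same heading also covers exit interviews and adverse events, so position under it does not establish that a row is an outcome measure.

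A second objection is that this is a copied row and not an intended exposure. The phone call moved as a whole column, which does not show that every row was reviewed, and footnote 2 is shared by both tables. That is plausible, but it explains the error without removing it.

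Third, the body text says controls receive the intervention after six months, which implies a dietitian assessment at crossover. Harm arises only if staff follow the table over the text. This stands in part: the documents do not show which staff follow. But the schedule is the operational instruction, and nothing in the text corrects it.

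Fourth, footnote 2 allows 14 days either side of enrollment, so the gap could be longer than 174 days. Consent and randomization both occur at Visit 1, so a study contact before Day 1 is implausible.

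What stands fully is that the effect is unsized, and that 60 of 60 is what the table schedules, not an observed exposure. The FitBit and step-ceiling points do not bear on the seriousness of the main one. Removing the FitBit mark outright could also cost control-arm step counts, which the secondary endpoint in section 3 uses, so that correction has to be conditional.

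**Conclusion.** The concern holds. Table 2 contradicts sections 1.2, 4.1, 6.1.1 and 6.3 and its own caption. As written, it schedules an intervention component for all 60 controls at baseline, 146 to 174 days before their intervention starts, and schedules none from Visit 2 on, against one at the start of intervention in Arm 1.

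The conflict between table and text is certain. Its effect on the results is not: it depends on staff having followed the table, it concerns one contact, and nothing in the documents allows the bias to be estimated. The expected direction for the 6-month comparison is toward a smaller difference, assuming the contact has some effect on diet. This should be corrected, though it does not by itself invalidate the comparison.

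**What to change.** By amendment:

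- In Table 2, move the Dietician Assessment mark from Visit 1 to Visit 2, and state footnote 2 for that arm as within 14 days of Visit 2.
- Remove the Visit 1 FitBit mark from Table 2. If controls do wear a FitBit before Visit 2 to measure step counts, keep the mark and state that the device is given without goals or feedback.
- In section 6.1.1, state the step ceiling as 10,000 per day, if that is what is meant, and give the 800-step increment in the same daily unit.
- If any control has already had a baseline dietitian contact under Table 2, record its date and report the number.

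The cost is a correction to the table and text. No procedures are added.

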6.3 MEASURES TO MINIMIZE BIAS: RANDOMIZATION AND BLINDING

Participants in this trial will be randomized to either the intervention arm (tailored physical activity and nutritional counseling) or a wait-list control arm that receives usual care for 6 months, after which they will receive the intervention (for 6 months). Neither participants nor interventionists are blinded to study arm.

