9.3.3 ANALYSIS OF THE SECONDARY ENDPOINT(S)

Analysis of secondary endpoints are not dependent on findings of primary endpoint.

-% weight loss: at month 6

-Physical activity: ≥10% increase in total minutes/week of physical activity based on IPAQ at month 6

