10.2 PROTOCOL AMENDMENT HISTORY

The table below is intended to capture changes of IRB-approved versions of the protocol, including a description of the change and rationale. A **Summary of Changes** table for the current amendment is located in the **Protocol Title Page**.

Version	Date	Description of Change	Brief Rationale
2.0	10-31-2019	Change of Principal Investigator's name	N/A
2.0	10-31-2019	Extended the time frame in which the VCTE can be done up to 14 days from enrollment date. If not enough time during enrollment, participants will be sent a link via email to complete the surveys within 14 days from enrollment date.	Extending the time frame in which participants can have the VCTE up to two weeks from their enrollment into the study will make participation in the study more convenient for subjects by shortening the length of the visit. Additionally, in the instances where VCTE is not available on the days or times subjects are enrolled into our study, this will give us the flexibility to schedule them in for a different day. Allowing participants to complete the surveys online will help increase efficiency and speed of enrollment.

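### The baseline CAP scan, and possibly the baseline IPAQ, may be taken up to 14 days after open-label randomisation and the start of the intervention

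*Combined protocol and SAP*

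**What the plan says.** Section 1.3, Table 1 (Arm 1) places consent, randomisation and the item "Provide FitBit and Instruction to Intervention Arm" at Visit 1, Day 1, in the same column as every baseline assessment.

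Footnote 1, marked on the VCTE row of both tables, lets a scan from the prior 6 months serve as baseline if weight has changed by less than 5%. It then adds: "Otherwise, VCTE will be performed +/- 14 days from enrollment".

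Footnote 4 deals with the questionnaires: "If not enough time during enrollment, participants will be sent a link via email to complete the surveys within 14 days from enrollment date". As printed, its marker stands on the survey rows of Table 2 (wait-list) only.

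The amendment history (section 10.2) shows that the later window was intended: "Extended the time frame in which the VCTE can be done up to 14 days from enrollment date". The reasons given are convenience, scanner availability and speed of enrolment.

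Section 6.3 states: "Neither participants nor interventionists are blinded to study arm". Section 6.1.1 has Arm 1 instructed in FitBit use and given an educational folder, and adds "Feedback will occur weekly for the first 3 months of the intervention". The nutritional assessment may also take place in the first two weeks.

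The primary endpoint (sections 3 and 9.3.2) is a CAP reduction of at least 5% at 6 months. For physical activity, section 9.3.3 uses a threshold of at least a "10% increase in total minutes/week of physical activity based on IPAQ at month 6", whereas sections 3 and 4.1 refer to step counts.

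**The concern.** Both responder definitions are percentage changes, so the baseline is the denominator. If it is taken after the participant knows the arm and Arm 1 has begun the programme, part of any real response is already inside it and is not counted as change. For CAP, that pulls the Arm 1 result toward no effect. For a self-reported measure such as the IPAQ, knowing the arm can also alter the answer, in either direction.

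No section requires the baseline scan or survey to come before randomisation, disclosure of the arm or FitBit handover. Section 9.3.2 has no rule for a late baseline, and its missing-data text covers only participants who lack follow-up imaging.

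**Working it through.** **Inputs from the documents**
- Randomisation and FitBit start in Arm 1: Visit 1, Day 1 (Table 1).
- Latest baseline VCTE: 14 days after enrolment (footnote 1). Enrolment is not formally defined. I read it as Visit 1, because the schedule and section 6.1.1 treat enrolment as that visit.
- Interval to Visit 2: 168 days. The late half of the window is 14/168 = 8.3% of it.
- Thresholds: 5% for CAP (sections 3, 9.1, 9.3.2) and 10% for IPAQ (section 9.3.3).

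**Inputs the documents do not give**
- The true change in CAP or activity by the time a late baseline is taken, and the share of participants with a late baseline. The values of b and g below are assumptions.

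**Step 1: sequence.** In Arm 1 the plan permits this order: randomisation, FitBit and folder on Day 1; weekly feedback and possibly the dietician session in days 1 to 14; baseline scan by day 14. Nothing in the plan rules it out.

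**Step 2: CAP.** Let b be the fraction by which CAP has already fallen when the baseline is measured. To register a fall of at least 5%, the month-6 value must be at most 0.95(1 − b) of the true pre-treatment value. The true fall needed is 1 − 0.95(1 − b).

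| Assumed b | True fall needed |
|---|---|
| 0 | 5% (the stated threshold) |
| 0.5% | 5.5% |
| 1% | 5.95% |
| 2% | 6.9% |
| 3% | 7.85% |

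**Step 3: IPAQ, if footnote 4 covers Arm 1.** Let g be the fraction by which reported activity has already risen. The true rise needed to register at least 10% is 1.10(1 + g) − 1. With g = 0 this is 10%. With an assumed g = 10% it is 1.10 × 1.10 − 1 = 21%.

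**Step 4: IPAQ, if footnote 4 covers only the wait-list arm.** Arm 1 then completes the IPAQ at Visit 1 while some controls complete it up to 14 days later. No step goals have contaminated the controls' answers, but baseline timing and knowledge of the arm differ between the groups.

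**Step 5: power.** Section 9.2 gives no responder rates, standard deviation or test for its 120 participants. That figure cannot be reproduced, and a loss of power from late baselines cannot be derived from the documents. The concern is about timing and does not depend on the sample size.

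**The case against.** The case for leaving the plan alone has weight. The window was a deliberate feasibility choice. Participants with an eligible historical scan, or scanned before allocation, are unaffected. Two weeks of lifestyle change probably move CAP little, and the resulting bias is toward no effect, so it would not by itself create a false positive. All of this stands and limits the size. It does not remove the permitted sequence.

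A reader might go further in three ways that the documents do not support.

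- *That the weekly step goal uses up the IPAQ endpoint.* Section 6.1.1 sets step goals rising 10% per week. Compounding two weeks gives 1.1² − 1 = 21% inflation of the baseline and a required true rise of 1.1 × 1.21 − 1 = 33.1%. But steps are not IPAQ minutes, full adherence from the first day is assumed, and section 6.1.1 suggests that tracked data come before the first tailored goal. On the same premise, 1.331 = 1.1³, so one further week of compliance would reach the raised threshold. Footnote 4 may not cover Arm 1, section 6.1.1 places the IPAQ at enrolment without repeating the allowance, and the step-count endpoint of sections 3 and 4.1 is not touched by survey timing.
- *That contamination can occur only in Arm 1.* Table 2 also ticks the dietician assessment and FitBit provision at Visit 1 for the wait-list arm, although the FitBit row is labelled for the intervention arm. One-sidedness cannot be asserted until that is reconciled.
- *That disappointed controls will skip the late scan.* Nothing in the documents shows this. Controls are promised the intervention at month 6, and payment follows completion of each visit's data collection.

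**Conclusion.** The point holds, at modest size. As written, the plan allows the baseline of the primary endpoint to be measured after open-label allocation and after treatment has begun, for Arm 1 participants without a usable prior scan. True early response would bias their change toward no effect. Over two weeks the CAP effect is unknown and probably small: the true fall needed moves from 5% to between 5.5% and 7.85% for assumed early falls of 0.5% to 3%.

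For the IPAQ version of the activity endpoint, the consequence depends on how far footnote 4 reaches. Its wording and the amendment history say participants, without limiting the arm, so covering both arms is a reasonable reading. On that reading the baseline can be contaminated or reported with knowledge of the arm; on the narrower reading its timing differs by arm. The 21% figure is an illustration resting on an assumed 10% early rise, not an estimate. The conclusion also rests on reading enrolment as Visit 1.

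**What to change.** - Amend footnotes 1 and 4 so that the baseline VCTE, or an eligible historical scan (which stays allowed), and at least the IPAQ are completed after consent but before randomisation, disclosure of the arm, FitBit handover and counselling.
- Keep the 14-day allowance and the e-mail link. Where the scan or survey cannot be done at the enrolment visit, defer randomisation to the return VCTE visit or to survey completion.
- Record the date of every baseline assessment and of randomisation.
- For participants already enrolled, add to section 9.3.2 a sensitivity analysis that excludes baselines taken after randomisation.
- Reconcile marker 4 between Tables 1 and 2, and the FitBit tick at Visit 1 in Table 2 with its row label.

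The cost is a short amendment, a delay of up to 14 days in randomisation and start for some participants, and possibly one extra contact for FitBit set-up where only the surveys were late. A late scan already requires a return visit, which can serve for randomisation and handover. The sample size does not change.
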